### 9.3.2. Primary Endpoint(s)/Estimand(s) Analysis

The primary endpoint is based on the percentage of participants showing a 50% response on each month, defined as showing 50% or fewer migraine headache days within the month than was seen during the baseline period. The primary estimand of interest is the overall mean monthly 50% response rate across the 3-month double-blind period attributable to the randomized treatment based on all available data as estimated from the GLIMMIX model. Here all available monthly migraine headache data will contribute to analysis as long as baseline monthly migraine headache day values are available. Any migraine headache day data collected after study intervention discontinuation but within the double-blind period will still be used within the analysis.

The primary analysis method will be the GLIMMIX given in Section 9.3.1 above for binary data. If the sample size is increased as a result of the interim analysis, the CHW procedure (Cui et al. 1999) will be applied to the primary endpoint to control the type I error at a one-sided  $\alpha = 0.025$  significance level. The CHW method ensures strong control of type I error when the sample size is increased in a data dependent manner.

If the sample size is increased as a result of the interim analysis, an unadjusted point estimate for the primary efficacy analysis will be calculated and reported. A median unbiased point estimate and a stage-wise adjusted confidence interval for the primary efficacy analysis will be calculated and reported based on the approach described by Brannath et al. (2009) to assess sensitivity of the point estimate.

### 9.3.3. Secondary Endpoints/Estimands Analysis

For all secondary endpoints, a similar estimand to the one used for the primary analysis will be employed. That is, the estimand of interest will be based on mean monthly estimates across/within the double-blind period and will be based on all available data during that period (even if collected after study intervention discontinuation). Additionally, baseline values must also be available.

The corresponding analyses for each of these endpoints will be as stated within Section 9.3.1 based on the type of endpoint measured (that is, binary or continuous).

If the sample size is increased, the CHW test statistic will be calculated for the key secondary endpoints before applying multiple testing procedure.

#### **9.3.4. Safety Analyses**

The safety and tolerability of treatment will be assessed by summarizing the following:

- TEAEs
- SAEs
- AEs leading to discontinuation
- AEs related to injection sites
- vital signs
- laboratory measurements

Unless specified otherwise, the categorical safety analyses will include both scheduled and unscheduled visits. Comparisons between treatment groups for all categorical safety measures will be made using Fisher's exact test within the safety population.

##### **9.3.4.1. Treatment-Emergent Adverse Events**

TEAEs are defined as the reported AEs that first occurred or worsened during the postbaseline period compared with the baseline period. For each TEAE, the reported severity level of the event (mild, moderate, or severe) will be determined by physician opinion. The MedDRA LLT will be used in the treatment-emergent computation. For each LLT, the maximum severity at baseline will be used as the baseline severity. If the maximum severity during postbaseline is greater than the maximum baseline severity, the event is considered to be treatment-emergent for the specific postbaseline period. Safety analyses for each study period will use all visits up through the last scheduled visit in the prior study period as baseline. For each participant and TEAE, the maximum severity for the MedDRA level being displayed (preferred term, High-Level Term, or System Organ Class [SOC]) is the maximum postbaseline severity observed from all associated LLTs mapping to that MedDRA level.

For events that are sex-specific, the denominator and computation of the percentage will include only participants from the specific sex.

##### **9.3.4.2. Vital Signs**

Vital signs collected during the study include systolic and diastolic blood pressure, pulse, and temperature. For vital signs procedures see Section [8.2.2](#).

The number and percentage of participants meeting criteria for treatment-emergent abnormalities in vital signs at any time during study will be summarized. Treatment group comparisons will be performed using Fisher's exact test.

##### **9.3.4.3. Laboratory Tests**

The incidence rates of participants with treatment-emergent abnormal, high, or low laboratory values at any time postbaseline will be assessed using Fisher's exact test for each laboratory test.

### **9.3.5. Other Analyses**

Details of analyses of other endpoints not falling under either efficacy or safety will be provided within the SAP.

## **9.4. Interim Analysis**

One interim analysis is planned for this study. The interim analysis will occur during Study Period III (double-blind treatment); this may result in increasing the sample size or continuing with the planned sample size. Details will be documented in the SAC SAP and ERB supplement.

To minimize the potential bias that results from performing an interim analysis, the interim analysis for this study will be conducted by a SAC external to the study team.

Only the SAC is authorized to evaluate unblinded interim analyses results to make an informed decision. Study sites will receive information about interim results ONLY if they need to know for the safety of their patients.

Unblinding details will be specified in the unblinding plan section of the SAP or a separate unblinding plan document.

## **9.5. Sample Size Determination**

The study will screen an estimated 1150 potential study participants to ensure a minimum of approximately 575 randomized participants. Based on the assumption of treatment difference of 12%, the minimum sample size of approximately 575 provides more than 85% power at a two-sided significance level of 5% and a dropout rate of no more than 10%, with the opportunity to increase the final sample size at the interim analysis if indicated to maintain a well-powered study. To preserve blinding, details of the sample size and power calculations are omitted from this protocol and are provided to the ERB in a separate document. If the interim is not performed, then the trial will enroll to a sample size as specified in the ERB document.

## 10. Supporting Documentation and Operational Considerations

### 10.1. Appendix 1: Regulatory, Ethical, and Study Oversight Considerations

#### 10.1.1. Regulatory and Ethical Considerations

- This study will be conducted in accordance with the protocol and with the following:
  - Consensus ethical principles derived from international guidelines including the Declaration of Helsinki and Council for International Organizations of Medical Sciences (CIOMS) International Ethical Guidelines
  - Applicable ICH GCP Guidelines
  - Applicable laws and regulations
- The protocol, protocol amendments, ICF, IB, and other relevant documents (for example, advertisements) must be submitted to an IRB/IEC by the investigator and reviewed and approved by the IRB/IEC before the study is initiated.
- Any amendments to the protocol will require IRB/IEC approval before implementation of changes made to the study design, except for changes necessary to eliminate an immediate hazard to study participants.
- Protocols and any substantial amendments to the protocol will require health authority approval prior to initiation except for changes necessary to eliminate an immediate hazard to study participants.
- The investigator will be responsible for the following:
  - Providing written summaries of the status of the study to the IRB/IEC annually or more frequently in accordance with the requirements, policies, and procedures established by the IRB/IEC.
  - Notifying the IRB/IEC of SAEs or other significant safety findings as required by IRB/IEC procedures.
  - Providing oversight of study conduct for participants under their responsibility and adherence to requirements of 21 Code of Federal Regulations (CFR), ICH guidelines, the IRB/IEC, European regulation 536/2014 for clinical studies (if applicable), and all other applicable local regulations.
- Investigator sites are compensated for participation in the study as detailed in the CTA.

#### 10.1.2. Informed Consent Process

- The investigator or his/her representative will explain the nature of the study, including the risks and benefits, to the participant, and answer all questions regarding the study.

- Participants must be informed that their participation is voluntary. Participants will be required to sign a statement of informed consent that meets the requirements of 21 CFR 50, local regulations, ICH guidelines, privacy and data protection requirements, where applicable, and the IRB/IEC or study center.
- The medical record must include a statement that written informed consent was obtained before the participant was entered in the study and the date the written consent was obtained. The authorized person obtaining the informed consent must also sign the ICF.
- Participants must be reconsented to the most current version of the ICF(s) during their participation in the study.
- A copy of the ICF(s) must be provided to the participant and is kept on file.

Participants who are rescreened are required to sign a new ICF.

#### **10.1.3. Data Protection**

- Participants will be assigned a unique identifier by the sponsor. Any participant records, datasets or tissue samples that are transferred to the sponsor will contain the identifier only; participant names or any information which would make the participant identifiable will not be transferred.
- The participant must be informed that his/her personal study-related data will be used by the sponsor in accordance with local data protection law. The level of disclosure must also be explained to the participant who will be required to give consent for his/her data to be used as described in the informed consent.
- The participant must be informed that his/her medical records may be examined by Clinical Quality Assurance auditors or other authorized personnel appointed by the sponsor, by appropriate IRB/IEC members, and by inspectors from regulatory authorities.
- The sponsor has processes in place to ensure data protection, information security and data integrity. These processes include appropriate contingency plan(s) for appropriate and timely response in the event of a data security breach.

#### **10.1.4. Committees Structure**

Potential cardiovascular events will be adjudicated by an external CEC. The role of the CEC is to adjudicate defined clinical events in a blinded, consistent, and unbiased manner throughout the course of a study. The purpose of the CEC for adjudication of cardiovascular events is to ensure that all reported events are evaluated uniformly by a single group.

Death, resuscitated cardiac arrest, and potential treatment-emergent cardiovascular events from the CRF will be identified using a search strategy based on the 9 MedDRA SMQs listed below. Narrow terms from these SMQs will be adjudicated if they are reported as a SAE. Potential non-serious cardiovascular events may be selected for adjudication following blinded medical review. Details of membership, operations, recommendations from the Committee, and the communication plan will be documented in the charter.

Narrow terms in the following SMQs will be adjudicated:

- Cardiac arrhythmias (includes sub SMQs; SMQ 20000049)
- Cardiac failure (SMQ 20000004)
- Cardiomyopathy (SMQ 20000150)
- Central nervous system vascular disorders (includes sub SMQs; SMQ 20000060)
- Embolic and thrombotic events (includes sub SMQs; SMQ 20000081)
- Hypertension (SMQ 20000147)
- Ischemic heart disease (includes sub SMQs; SMQ 20000043)
- Pulmonary hypertension (SMQ 20000130)
- Torsade de pointes/QT prolongation (SMQ 20000001)

Case unblinding may be performed for above reviews, only if necessary

#### **10.1.5. Dissemination of Clinical Study Data**

A clinical study report will be provided for this study and a summary of study information provided on publicly available websites.

#### **10.1.6. Data Quality Assurance**

- All participant data relating to the study will be recorded on electronic CRFs unless transmitted to the sponsor or designee electronically (for example, laboratory data). The investigator is responsible for verifying that data entries are accurate and correct by signing the CRF.
- The investigator must maintain accurate documentation (source data) that supports the information entered in the CRF.
- The investigator must permit study-related monitoring, audits, IRB/IEC review, and regulatory agency inspections and provide direct access to source data documents.
- QTLs will be pre-defined to identify systematic issues that can impact participant safety and/or reliability of study results. These pre-defined parameters will be monitored during the study and important excursions from the QTLs and remedial actions taken will be summarized in the clinical study report.
- Monitoring details describing strategy (for example, risk-based initiatives in operations and quality such as risk management and mitigation strategies and analytical risk-based monitoring), methods, responsibilities and requirements, including handling of noncompliance issues and monitoring techniques are provided in the monitoring plan.
- The sponsor or designee is responsible for the data management of this study including quality checking of the data.

- The sponsor assumes accountability for actions delegated to other individuals (for example, contract research organizations).
- Study monitors will perform ongoing source data verification to confirm that data entered into the CRF by authorized site personnel are accurate, complete, and verifiable from source documents; that the safety and rights of participants are being protected; and that the study is being conducted in accordance with the currently approved protocol and any other study agreements, ICH GCP, and all applicable regulatory requirements.
- Records and documents, including signed ICFs, pertaining to the conduct of this study must be retained by the investigator for the time period outlined in the CTA unless local regulations or institutional policies require a longer retention period. No records may be destroyed during the retention period without the written approval of the sponsor. No records may be transferred to another location or party without written notification to the sponsor.
- In addition, sponsor or its representatives will periodically check a sample of the participant data recorded against source documents at the study site. The study may be audited by sponsor or its representatives, and/or regulatory agencies at any time. Investigators will be given notice before an audit occurs.

### **Data Capture System**

The investigator is responsible for ensuring the accuracy, completeness, legibility, and timeliness of the data reported to the sponsor.

An EDC system will be used in this study for the collection of CRF data. The investigator maintains a separate source for the data entered by the investigator or designee into the sponsor-provided EDC system. The investigator is responsible for the identification of any data to be considered source and for the confirmation that data reported are accurate and complete by signing the CRF.

Additionally, eCOA data (participant-focused outcome instrument) will be directly recorded by the participant into an instrument (handheld smart phone and/or tablet). The eCOA data will serve as the source documentation and the investigator does not maintain a separate, written or electronic record of these data.

Data collected via the sponsor-provided data capture system(s) will be stored at third parties. The investigator will have continuous access to the data during the study and until decommissioning of the data capture systems. Prior to decommissioning, the investigator will receive an archival copy of pertinent data for retention.

Data managed by a central vendor, such as laboratory test data, will be stored electronically in the central vendor's database system and reports or electronic transfers will be provided to the investigator for review and retention. Data will subsequently be transferred from the central vendor to the sponsor data warehouse.

Data from complaint forms submitted to sponsor will be encoded and stored in the global PC management system.

**10.1.7. Source Documents**

- Source documents provide evidence for the existence of the participant and substantiate the integrity of the data collected. Source documents are filed at the investigator's site.
- Data entered in the eCRF that are transcribed from source documents must be consistent with the source documents or the discrepancies must be explained. The investigator may need to request previous medical records or transfer records, depending on the study. Also, current medical records must be available.
- Definition of what constitutes source data can be found in Section [10.1.6](#).

**10.1.8. Study and Site Start and Closure****First Act of Recruitment**

The study start date is the date on which the clinical study will be open for recruitment of participants.

The first act of recruitment is the first participant visit and will be the study start date.

**Study or Site Termination**

The sponsor designee reserves the right to close the study site or terminate the study at any time for any reason at the sole discretion of the sponsor. Study sites will be closed upon study completion. A study site is considered closed when all required documents and study supplies have been collected and a study-site closure visit has been performed.

The investigator may initiate study-site closure at any time, provided there is reasonable cause and sufficient notice is given in advance of the intended termination.

Reasons for the early closure of a study site by the sponsor or investigator may include but are not limited to:

For study termination:

- Discontinuation of further study intervention development

For site termination:

- Failure of the investigator to comply with the protocol, the requirements of the IRB/IEC or local health authorities, the sponsor's procedures, or GCP guidelines
- Inadequate recruitment (evaluated after a reasonable amount of time) of participants by the investigator
- Total number of participants included earlier than expected

If the study is prematurely terminated or suspended, the sponsor shall promptly inform the investigators, the IECs/IRBs, the regulatory authorities, and any contract research organization(s) used in the study of the reason for termination or suspension, as specified by the applicable regulatory requirements. The investigator shall promptly inform the participant and should assure appropriate participant therapy and/or follow-up.

**10.1.9. Publication Policy**

In accordance with the sponsor's publication policy, the results of this study will be submitted for publication by a peer-reviewed journal.

**10.1.10. Investigator Information**

Physicians with a specialty in neurology, headache specialist, or other physicians with experience in headache clinical trials and diagnosing and treating migraine participants will participate as investigators in this clinical trial.

## 10.2. Appendix 2: Treatments Allowed and Treatments not Allowed as Concomitant Therapy

### **A. Medications allowed for the ACUTE treatment of migraine headaches or other pain or injury:**

Acetaminophen (paracetamol), NSAIDs; Triptans; Ergotamine and derivatives; aspirin, caffeine, and acetaminophen combination; or combinations thereof. For acetaminophen, the maximal allowed dose will be 3 g/day from all acetaminophen-containing medicinal products.

The following medications are allowed with restrictions:

1. Opioid and barbiturates no more than 4 days/month.
2. Single dose of injectable steroids allowed only once during the study, in an emergency setting (SP II and III).

**B. Medications, procedures or devices not allowed for any reason/indication during SP II and III:**

Acetazolamide  
Acupuncture  
Anticonvulsants/Antiepilepticsa  
Antipsychotics  
Beta-blockers  
Botulinum toxin applied to head/neck area for therapeutic use  
Cannabis/Cannabinoidsb  
Chiropractic procedures, physiotherapy, TENS or other electric devices on head and neck  
Corticosteroids for oral usec  
CYP3A4: Moderate and strong inhibitors of CYP3A4 (includes Paxlovid)d  
CYP3A: Moderate and strong inducers of CYP3A  
Efflux transporters: Inhibitors of P-gp and BCRP  
Flunarizine  
Herbals with anti-inflammatory effect (feverfew, willow bark, petasites/butterbur), herbals with sympathomimetic effect (ma huang, ephedra, bitter orange, synephrine) and herbals with catecholamine transmitter reuptake inhibition (St. John's Wort)  
Migravent  
Monoamine oxidase inhibitors (MAOIs)  
Memantine  
Neurotropin®  
Nerve block in head/neck area  
Serotonin 5HT2a/2c antagonists, for example: nefazodone  
Tizanidine  
Tricyclic antidepressants (TCAs)  
Triptans for prophylaxis of menstrual-related migraine  
Venlafaxine and desvenlafaxine  
Verapamil

**C. Restricted medication during SP II and III: Use of the following medications for indications other than migraine prevention is allowed providing the dose is stable 2 months prior to Visit 2 and is expected to remain stable during Visit 2 through 6.**

ACE inhibitors  
Angiotensin receptor blockers (ARBs)  
Benzodiazepines  
Bupropion  
Calcium-channel blockers (except verapamil and flunarizine)  
Clonidine

Gabapentin  
Guanfacine  
Mirtazapine  
Pregabalin  
SSRIs/NRIs/SNRIs (other than venlafaxine)  
Stimulants (prescription strength), for example: methylphenidate, dextroamphetamine, mixed amphetamine salts  
Trazadone (for sleep only and must be taken in a stable fashion)  
Use of electric devices (that is, TENS), physiotherapy, chiropractic procedures on low back and extremities

**D. Restricted medication during SP II-III: Use of the following medications for indications other than migraine prevention is allowed:**

Beta-blockers, ophthalmic

Cyproheptadine

Melatonin

Abbreviations: 5HT = 5-hydroxytryptamine; ACE = angiotensin-converting enzyme; NRI = norepinephrine reuptake inhibitor; NSAID = nonsteroidal anti-inflammatory drug; SNRI = serotonin-norepinephrine reuptake inhibitor; SP = Study Period; SSRI = selective serotonin reuptake inhibitor; TENS = transcutaneous electrical nerve stimulation.

- a Gabapentin and pregabalin may be allowed if the criteria in Part C are met.
- b It may be allowed in the study if prescribed for a condition other than migraine or headache, as long as the use of Cannabis/Cannabinoids is not expected to affect the interpretation of study results or the safety of the participant. The usage should remain consistent for the duration of the study and criteria in exclusion 23ii are met.
- c Topical and inhaled corticosteroids allowed for conditions other than migraine or headache.
- d Paxlovid is authorized by the FDA for emergency use for treatment of mild-to-moderate COVID-19 and contains ritonavir - a strong CYP3A4 inhibitor; thus, is excluded in CGBD.

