		Missing safety measurement: Chemistry or Hematology at baseline or in SP III	Programmable – Stats	
For randomized patients, if calcium and hemoglobin are missing all baseline measures, or if there is non-missing Visit 6 or early termination data and missing the post-baseline measures in the double-blind treatment period.
 
For patients who discontinued due to "lost to follow up", if all post-baseline measures are missing, it is not an important protocol deviation.

Document: CCI

Author: PPD

Version Number: 3.0

Version Date: 19May2023

Category	Subcategory	Study-specific	Source	Comments
Data Quality	Missing Date	Missing safety measurement: ECGs at baseline and in SP III	Non-programmable-Monitor identified	Same rule as for "Missing safety measurement: Chemistry or hematology at baseline or in SP III".
		Missing hepatic follow-up labs	Non-Programmable-Study Team identified	
	Treatment Assignment/ Randomization Error	IWRS data entry errors that impact patient stratification	Programmable – Stats	If migraine headache day categories (<8 vs ≥8) from IWRS was different from derived from ePRO.
Study Procedures	Discontinuation	Participant met at least one criterion for Study intervention discontinuation, but continued with dosing	Non-programmable-Monitor identified	
		Participant met at least one criterion for Study discontinuation, but continued in the study with dosing	Non-programmable-Monitor identified	
	Excluded Conmeds	Taking prohibited migraine preventive medication for primary study indication for >7 consecutive days during SP II or III	Programmable - Stats	Prior therapy should be excluded in the consideration.
		Taking prohibited migraine preventive medication for any indication for >7 consecutive days during SP II or III	Programmable - Stats	Prior therapy should be excluded in the consideration.

Document: CCI

Author: PPD

Version Number: 3.0

Version Date: 19May2023

Category	Subcategory	Study-specific	Source	Comments
Study Procedures	Excluded Conmeds	Taking Botulinum toxin A and B in the head or neck for therapeutic indication during SP II or III	Non-Programmable- Study Team identified	1) Stats will create the list of patients meet this IPD criteria. 2) Among those, the true IPDs will be manually added into non-programmable excel sheet.
		Opioid, barbiturate, or steroid use >7 consecutive days during SP II or III	Programmable - Stats	Prior therapy should be excluded in the consideration.

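### Protocol Appendix 2 gives desvenlafaxine two statuses: Part B bars it outright, while the Part C class entry allows stable-dose SNRIs and excepts only venlafaxine

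*Protocol*

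**What the plan says.** Protocol Section 6.8 sends sites to Section 10.2 (Appendix 2) to see what is and is not permitted. Part B there is headed "Medications, procedures or devices not allowed for any reason/indication during SP II and III" and includes the entry "Venlafaxine and desvenlafaxine", to which no footnote is attached.

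Part C sets a conditional permission: "Use of the following medications for indications other than migraine prevention is allowed providing the dose is stable 2 months prior to Visit 2", with the dose expected to stay stable through Visit 6. One of its entries is "SSRIs/NRIs/SNRIs (other than venlafaxine". The parenthesis closes there, so venlafaxine is the only exception. The abbreviation note gives "SNRI = serotonin-norepinephrine reuptake inhibitor" but does not list the members of the class.

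Four other places depend on these lists:

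- Protocol Section 4.1.1 requires participants to stop excluded medications.
- Protocol Section 5.2, criterion 13, lets people with stable major depressive disorder, an anxiety disorder or bipolar disorder be considered only if they take no excluded medication.
- SAP Appendix 3 makes this an important protocol deviation: "Taking prohibited migraine preventive medication for any indication for >7 consecutive days during SP II or III".
- SAP Section 9.2 says the clinical team will help identify the excluded medications for that check. The SAP carries no drug list of its own.

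**The concern.** Take a participant on a long-standing, stable dose of desvenlafaxine for depression. Read from Part B, this person is on a barred drug. Read from Part C, the person meets the stated condition for continuing it. The two parts belong to the same appendix and cover the same study periods.

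The participants most likely to raise the question are those criterion 13 is written for, since it admits stable mood and anxiety disorders subject to the medication lists. Section 5 permits no waivers, so a site cannot settle the point by exception. Under one reading the participant must stop an established treatment or stay out of the trial. Under the other, the participant continues it. The same doubt carries over to the table of important deviations, which the SAP reports by randomized arm.

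**Working it through.** The plan states no figure on this point, so the check is a comparison of texts.

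**1. Class membership.** The documents do not state that desvenlafaxine is an SNRI. That is basic drug classification. It also fits the text: Part B pairs the drug with venlafaxine, which Part C treats as a member of its SSRI/NRI/SNRI group by excepting it.

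**2. Each part applied to stable-dose desvenlafaxine taken for depression.**

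| | Part B | Part C |
|---|---|---|
| Scope | Study Periods II and III, whatever the indication | Study Periods II and III, other than to prevent migraine, at a stable dose |
| Relevant entry | "Venlafaxine and desvenlafaxine" | "SSRIs/NRIs/SNRIs (other than venlafaxine" |
| Result | Not allowed | Allowed |

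**3. Search for a tie-breaker.** Footnotes a to d of Appendix 2 cover anticonvulsants, cannabis, corticosteroids and Paxlovid. None mentions desvenlafaxine. Section 6.8 refers the reader to Section 10.2 without saying which part prevails.

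**4. How the appendix treats comparable overlaps.** The Part C entry "Calcium-channel blockers (except verapamil and flunarizine" excepts both drugs of that class that Part B names. For anticonvulsants, footnote a says: "Gabapentin and pregabalin may be allowed if the criteria in Part C are met". Footnote b does similar work for prescribed cannabis. The SNRI entry has an exception too, but it names only one of the two drugs in Part B. Its silence on the second can be read as permission.

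**5. Whether the SAP threshold filters these cases out.** The flag needs more than 7 consecutive days of use. Under the usual visit windows, a completer has at least 30 days of prospective baseline and reaches Visit 6 at 90 − 2 = 88 days or later: 30 + 88 = 118 days. A drug taken daily throughout passes the 7-day threshold easily. Whether it is flagged then depends on whether the clinical team counts it as a prohibited preventive.

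**6. Whether any analysis depends on it.** The ITT and safety sets (Protocol Section 9.2; SAP Sections 5.1 and 5.2) are defined by randomization and dosing, not by deviations. A per-protocol set appears in the protocol's abbreviation list but not among the analysis sets of either document. Under SAP Section 9.2, important deviations are tabulated and listed only.

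**The case against.** The best reply is that a specific ban overrides a general class permission. Part B names the drug under an absolute heading. Part C is a class entry, and where Part C is meant to lift a Part B ban, footnote a says so; desvenlafaxine has no such footnote. The appendix relies on specificity in at least one place: Part B bars beta-blockers and Part D permits the ophthalmic form, with no footnote linking them. The Amendment c history also records that desvenlafaxine was added to the table as a clarification of what is not allowed, which suggests that a matching edit to Part C was missed. Finally, Section 6.8 sends questions to the medical monitor.

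Much of this stands. It is a workable reading and may be what was intended. But the protocol states no such rule, and in the beta-blocker case no exception list points the other way. The amendment history explains how the mismatch may have arisen; it does not change the current text. The medical monitor helps only a site that notices a problem, and a site reading Part C alone sees a clear permission.

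A reader might infer more than the documents support:

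- **That sites did enrol participants inconsistently.** The documents show only that they could. Any list updates sent to sites are not visible here.
- **That the deviation flag turns mechanically on which list is programmed.** SAP Section 9.2 puts clinical-team input in between.
- **That Part B bars the drug because it could confound the migraine outcome.** Part B gives no such reason, and it also bars CYP3A4 inhibitors, CYP3A inducers and transporter inhibitors.

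**Conclusion.** Wrong as written, minor. Parts B and C give opposite answers for stable-dose desvenlafaxine taken for something other than preventing migraine, and nothing in the current text decides between them. The practical reach is eligibility under criterion 13, whether a participant must stop the drug under Section 4.1.1, and how its use is classed under SAP Appendix 3.

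The number affected cannot be stated: the documents give no prevalence of desvenlafaxine use, and any count out of the 575 planned participants would rest on an assumption with no basis in them. It would also go too far to treat this as a threat to the efficacy result, since no analysis set, power figure or primary analysis depends on it.

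The conclusion rests on one fact from outside the documents, that desvenlafaxine is an SNRI. It takes no position on which status is right.

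**What to change.** Reconcile Parts B and C of Appendix 2 so that desvenlafaxine has a single status. Either the Part C exception names the same two drugs as the Part B entry, or desvenlafaxine comes out of Part B. The choice is the sponsor's.

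Communicate the result to sites with the date from which it applies. Have the clinical team identify excluded medications for the SAP Appendix 3 flag from the reconciled list, so that use of the drug is classed the same way for every participant.

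The cost is a one-line correction, a notice to sites and a matching update to the clinical team's medication list. Section 6.8 says that changes to the lists are communicated to investigators and do not count as a protocol amendment.
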